3.1.2. Exclusion Criteria

Patients must not meet any of the exclusion criteria described below.

1) Patients who are not candidates for first-line treatment with a tyrosine kinase inhibitor.

2) Patients who are receiving the treatment as second-line or subsequent therapy.

3) Untreated hypothyroidism.

4) Untreated severe anaemia.

5) Pregnancy or breast-feeding.

6) Myocardial infarction or cerebrovascular accidents (CVA) within the last 6 months.

7) Severe hepatic impairment.

8) Concomitant use of potent inhibitors or inducers that interact with hepatic cytochrome CYP3A4.

QUALITY OF LIFE:

 Fatigue-related quality of life of patients evaluated using the validated 13-item FACIT-Fatigue scale for patients with kidney cancer in Spanish. Company FACIT.ORG (USA) (ANNEX 8). Quality of life in patients with palmar-plantar erythrodysaesthesia (hand-foot syndrome). To be evaluated according to CTCAE Version 4.0 Published: May 28, 2009 (v4.03: June 14, 2010) with scores running from 1 to 3 (see ANNEX 9).

SCHEDULE

Date of submission to AEMPS for classification: October 2015

Proposed date of submission to the IEC: November 2015

Proposed date of inclusion of the first patient in the study: February 2016

Proposed end-of-recruitment date: August 2017 or after recruiting 100 patients, whichever occurs first.

Recruitment period: 18 months.

Proposed date of the end of data collection: May 2018 or whenever the last patient passes to the 2nd line of treatment, whichever occurs first.

Expected date of Interim study report: After completing the 9 months of fatigue-related quality of life follow-up in all patients, estimated July 2018.

Expected date of Final study report: October 2018

SOURCE OF FUNDING

Pfizer SLU, as sponsor of the study, will provide financial compensation to the participating sites/investigators. Such compensation will be explicit and transparent, without prejudice to the internal rules of their employing agencies and in accordance with specific regulations in the ARs and at the sites where the study is conducted.

Fees are to fund the collection and transcription of clinical and epidemiological data from patients and the quality of life questionnaires to the case report forms.

AMENDMENTS AND UPDATES

None

Amendment No.	Date	Substantial or administrative amendment	Amended protocol section(s)	Summary of change(s)	Reason

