4. MILESTONES

Milestone	Proposed date
Start of data collection	
Proposed date of the first patient's first visit, FSFV	February 2016
End of data collection	
Proposed date of the last patient's last visit, LSLV	May 2018
Interim study report	
Proposed date of drafting (or remittance) of Interim report	July 2018
Final study report	
Proposed date of drafting (or remittance) of Final report	October 2018

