7. METHODS OF INVESTIGATION

7.1. Study design

Prospective, multicentre, observational, post-authorisation study in patients aged ≥ 18 years diagnosed with metastatic renal cell carcinoma who are to be given a tyrosine kinase inhibitor as first-line treatment.

The study will evaluate measures to improve patients' quality of life, such as time of drug administration, napping, temporary treatment breaks and dose reductions.

Fatigue-related quality of life will be evaluated using the Spanish version of the *FACIT*–Fatigue **Questionnaire**, which will be completed by the patient individually after having been explained by the clinician or a person appointed by the investigator (nursing staff, clinical trial coordinator)

in the treatment room or another room during the scheduled visits, once the patient understands how to complete the form.

The FACIT–Fatigue questionnaire will be handed out together with the patient diary at the following treatment times, which coincide with the visits, according to the department's protocol:

- 1) **Baseline** (before starting the treatment)
- 2) Month 3
- 3) Month 6
- 4) Month 9 or upon treatment discontinuation
- 5) Additional visits according to the oncology department's clinical practice: additional visits may be recorded on the case report form (e.g. at 15 days)

The patient will also complete this FACIT-Fatigue questionnaire at home **at the start of each cycle** (for sorafenib and pazopanib a cycle will be 6 weeks of treatment), even if this does not coincide with scheduled visits to the hospital.

The hand-foot syndrome-related quality of life evaluation that patients may be asked to take part in will be performed on the basis of the CTCAE V4.03 2010 with scores running from 1 to 3 (see ANNEX 9).

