For each patient, the safety event reporting period begins when the patient receives the first dose of sunitinib, sorafenib or pazopanib or signs the informed consent if he/she has already been exposed to sunitinib, sorafenib or pazopanib and it lasts until the end of the study observation period, which should cover at least 28 calendar days after the last administration of the study drug; a report must be sent to the Department of Drug Safety at Pfizer (or its appointed representative) in the event that any of the types of safety events listed in the above table occur during this period. In this study, for patients included retrospectively without signing the ICF, the reporting period will run from administration of the first dose until 28 calendar days after administration of the last dose. If a patient receives a study drug on the last day of the observation period, the reporting period should be extended 28 calendar days after the end of the observation period. The date of informed consent frequently coincides with the date of recruitment. In some situations, there may be a delay between the date of informed consent and the date of recruitment. In these situations, if a patient gives his/her informed consent but is never included in the study (e.g. the patient changes his/her mind about participating, screening failure, etc.), the reporting period ends on the date on which it is decided not to recruit the patient.

If the investigator is aware of an SAE occurring at any time after completion of the study and believes that the SAE is related to sunitinib, sorafenib or pazopanib, the SAE should also be reported to the Department of Drug Safety at Pfizer.

Causality assessment

The investigator is obliged to assess and record the causal link. For all AEs, the investigator should obtain sufficient information to determine the causality of each adverse event. For sunitinib, sorafenib or pazopanib-related AEs, the investigator is required to follow the AE until the event and/or its consequences are resolved or stabilised to an acceptable level from their point of view, and Pfizer agrees with that assessment.

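### The protocol requires safety observation to 28 days after the last dose, but schedules no contact to collect it and closes data collection without allowing for it

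*Protocol*

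**What the plan says.** - **Required window.** Protocol section 9 (Reporting period) sets a safety observation period "which should cover at least 28 calendar days after the last administration of the study drug". For a patient dosed on the last day of observation, "the reporting period should be extended 28 calendar days after the end of the observation period". The table at the start of section 9 puts all SAEs and all non-serious AEs on the CRF, separately from the 24-hour form to the sponsor's safety department.
- **Scheduled contacts.** Section 7.1 names baseline, month 3, month 6 and "Month 9 or upon treatment discontinuation". Visits made under local practice are optional: "additional visits may be recorded on the case report form". Neither 7.1 nor 7.2 sets a contact or CRF entry 28 days after the last dose.
- **Closure.** Section 3 (Schedule) ends data collection in "May 2018 or whenever the last patient passes to the 2nd line of treatment, whichever occurs first". Section 4 gives the same month as the "Proposed date of the last patient's last visit, LSLV". Neither mentions the 28 days.
- **Analysis.** SAP section 6.2 promises the incidence of serious adverse events. The SAP does not say over what period events are counted, and its list of tables (section 9) has no SAE table from which a period could be inferred.

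**The concern.** Section 9 imposes a requirement that sections 3, 4 and 7.1 neither schedule nor leave time for. The 24-hour clock in section 9 starts when the investigator becomes aware of an event, so it ensures that known events are reported but does not ensure that anyone looks. An event learned of after the CRF has closed can reach the safety database without reaching the study dataset.

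The weeks after stopping are not empty. Section 9 requires related AEs to be followed until resolved or stabilised, and it makes a death from the malignancy within the reporting period a grade 5 SAE. The window therefore matters for patients who stop at progression as well as for those who stop for toxicity. At stake are the completeness of the SAE and AE incidence in the final report and a clear rule on whether, say, an event on day 20 after the last dose counts.

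**Working it through.** **1. The plan's own closing date.** Inputs, all from Protocol section 3 (Schedule): first patient February 2016, recruitment 18 months, questionnaire follow-up 9 months.

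February 2016 + 18 months = August 2017, the stated end of recruitment. August 2017 + 9 months = May 2018, the stated end of data collection. The plan's figure is reproduced exactly, with no slack.

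**2. Add the 28 days.** Take closure as 31 May 2018, the latest reading of May. For a patient who stops at month 9:

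| Entry | Month 9 | Month 9 + 28 days |
|---|---|---|
| 1 August 2017 | 1 May 2018 | 29 May 2018 |
| 3 August 2017 | 3 May 2018 | 31 May 2018 |
| 4 August 2017 | 4 May 2018 | 1 June 2018 |
| 31 August 2017 | 31 May 2018 | 28 June 2018 |

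Entry from 4 August 2017 onward runs past closure. More generally, any last dose on or after 4 May 2018 does so, whenever the patient entered. A patient still on drug on 31 May has the section 9 extension to 31 May + 28 days = 28 June 2018.

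**3. How many windows are incomplete at closure (illustration).** Assumptions: entry uniform from 1 February 2016 to 31 August 2017 (577 days); exponential time on treatment with median m months of 30.4375 days. The values 9.2 and 11 months are the PFS figures in Protocol section 5, used as stand-ins for time on treatment; 6 months is a plain assumption. Closure falls 273 days after the last possible entry and 850 days after the first. With λ = ln 2 / (30.4375 m):

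- still on drug at closure: A = (e^(−273λ) − e^(−850λ)) / (577λ)
- window incomplete at closure: B = A × e^(28λ)
- stopped less than 28 days before closure: B − A

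| m | A | B | B − A | Complete, 1 − B |
|---|---|---|---|---|
| 6 | (0.3548 − 0.0397)/2.190 = 0.144 | 0.144 × 1.112 = 0.160 | 0.016 | 0.84 |
| 9.2 | (0.5088 − 0.1220)/1.428 = 0.271 | 0.271 × 1.072 = 0.290 | 0.019 | 0.71 |
| 11 | (0.5683 − 0.1721)/1.195 = 0.332 | 0.332 × 1.060 = 0.351 | 0.020 | 0.65 |

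Most of the incomplete windows belong to patients still on drug; about 2% of patients stopped in the last four weeks.

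**4. How many have the discontinuation visit as their last named visit.** On the same curve, the proportion stopping by month 9 is 1 − 2^(−9/m): 0.43 for m = 11, 0.49 for m = 9.2 and 0.65 for m = 6. For these patients the whole 28 days follow the last visit the protocol names, whatever their entry date. This gap is separate from the calendar one, and later closure alone would not fill it.

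**5. The alternative trigger.** If the last patient passes to second line before May 2018, collection ends then. Nothing requires that patient's last first-line dose to be 28 days back, nor that of anyone else who stopped shortly before.

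**The case against.** The strongest reply is that the duty is fully stated. Section 9 makes the 28 days part of the reporting period, extends it for patients dosed on the last day, and keeps open the case that begins "If the investigator is aware of an SAE occurring at any time after completion of the study" when the investigator believes the event is related. Section 8.2 calls for follow-up of unresolved events after withdrawal. Sections 7.2 to 7.4 draw on routine practice and medical records, and section 7.1 lists when the questionnaire is handed out, not when contact ends. SAP section 8.2.4 follows patients to the end of first line or to the cut-off. All of this stands, and it limits the point to how events are ascertained and when the CRF closes.

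Several stronger readings are tempting and are not supported:

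- *The window goes uncollected.* The reporting duty remains, and routine visits and records can supply events.
- *Each patient's collection stops at second line.* Section 3 refers to the last patient. It is a study-level close and can cut short only that patient's window and those of others who stopped in the preceding 28 days.
- *All 100 patients lose the window.* Under the assumptions above, 65% to 84% of windows are complete before the calendar close, and a window that follows the last named visit is not thereby unobserved.
- *Fatigue and hand-foot syndrome results are biased downward.* SAP section 8.2.3 and the table list summarise these at months 3, 6 and 9, so events after stopping largely fall outside those tables by design.

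It is also fair to say that the dates are labelled as proposed, that August 2017 is an upper limit on recruitment, and that the CRF itself (Annex 2) was not available, so an existing page covering this period cannot be ruled out.

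**Conclusion.** The inconsistency is real and of moderate weight. Section 9 requires 28 days of observation after the last dose with all events on the CRF; section 7.1 schedules nothing to collect them, and sections 3 and 4 close on a date that leaves no room. The patients mainly affected are those whose last visit is the discontinuation visit, those entering from about 4 August 2017, and those still on drug or recently stopped at closure.

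The calendar result needs only the protocol's own dates and a 31 May closure. The proportions (16% to 35% of windows incomplete at closure; 43% to 65% of patients stopping by month 9) rest on uniform entry and exponential treatment times with assumed medians, and show order of magnitude only. The main result exposed is the SAE and AE incidence promised in SAP section 6.2. The documents give no event rate for the four weeks after stopping, so the size of any undercount is unknown.

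**What to change.** 1. **Protocol 7.1 and 7.2:** add one CRF entry of AE and SAE status at 28 days after the last dose, or at 28 days after the end of observation for patients still on drug. Take it from routine records or ordinary clinic contact.
2. **Protocol 3 and 4:** keep the CRF open for safety data until 28 days after the end of observation, which is 28 June 2018 on the planned dates, and add 28 days to the second-line trigger. Do not tie closure to the last patient's last dose: with 14% to 33% possibly still on drug on 31 May 2018, that date is open-ended and could pass the planned reports.
3. **SAP 6.2:** count SAEs and AEs from first dose to 28 days after last dose, or to 28 days after the end of observation for those still on drug.

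The cost is one CRF page per patient and about four weeks' later safety closure, with no added test or study visit. The pressure point is the July 2018 interim report: from 28 June to 31 July is 33 days at most, against 61 from 31 May. The October 2018 final report is not threatened.

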9.1. Single reference safety document

The Summary of Product Characteristics of the medicinal product will be used as the single reference safety document (SRSD) during the study, which will be used by the Department of Drug Safety at Pfizer to evaluate any safety event reported to Pfizer by the Investigator during the course of the study.

The SRSD should be used by the investigator as a guideline for prescribing and evaluating any event relating to patient safety in relation to the drug received.

Evaluation of severity

The investigator will use the following definitions of severity according to version 4.0 of the CTCAE to describe the maximum severity of the adverse event. If the adverse event is serious, the CTCAE grade reported in the adverse events section of the CRF should match the description of the CTCAE grade included in the narrative section of the serious adverse event report.

GRADE	Clinical description of severity	
0	No change from the normal or reference range (this grade is not in version 4.0, but may be used in certain circumstances)	
1	MILD Adverse Event	
2	MODERATE Adverse Event	
3	SEVERE Adverse Event	
4	LIFE-THREATENING OR DISABLING Adverse Event	
5	DEATH RELATED TO an adverse event	

Note the distinction between the severity and seriousness of an adverse event. A severe event is not necessarily a serious event. For example, a headache may be severe (significantly interferes with the subject's normal functioning), but would not be classified as serious unless it met one of the serious adverse event criteria listed above.

The incidence of AEs leading to discontinuation of the investigational medicinal product and/or

Reporting requirements

An adverse event report form (*Non-Interventional Study (NIS) Adverse Event Monitoring (AEM) Report Form*) is included as annex 10 to the protocol, which, once COMPLETED, will be forwarded to the Department of Drug Safety at Pfizer Spain and the contact person for the study on behalf of the sponsor via the following communication channels:

To the Pharmacovigilance Department:

- By [contact]

- Or by email: [contact]

A copy should also be forwarded to the contact person for the study, either by fax: PPD or by email: PPD

10. PUBLICATION OF RESULTS

All information obtained as a result of this study will be considered confidential.

The Scientific Coordinator of the study, together with the sponsor, will undertake to disclose the results through the usual scientific means.

The authors listed in the publication of the study results must meet the following requirements:

• Substantial contribution to the proposal and design of the study or to the collection, analysis and interpretation of study data

• Involvement or contribution in writing and/or reviewing the publications with regard to intellectual content

• Contribution to final approval of the published version

• Agreement to act responsibly in all aspects of the publication of the data to ensure that issues relating to the accuracy or integrity of any part of the work are investigated and appropriately addressed

INCIDENT REPORTING

In the event that a ban or restriction (e.g. temporary suspension) is imposed by a competent authority in any part of the world, or if the investigator is aware of any new information that might influence the evaluation of the benefits and risks of a Pfizer product, Pfizer must be immediately informed thereof.

The investigator will also inform Pfizer immediately of any urgent safety measures taken to protect the study patients from any danger and any violation of the protocol of which he/she is aware.

12. LIST OF TABLES

Not applicable

13. LIST OF CHARTS

Not applicable

ANNEX 1. LIST OF INDEPENDENT DOCUMENTS

Number	Date	Title
Annex 1	N/A	List of Annexes to the Protocol
Annex 2		Case Report Form
Annex 3	N/A	Coordinating Investigators' Statement
Annex 4	N/A	Reference IEC Approval
Annex 5	Version 1.0	Patient Information Sheet/Informed Consent Form
Annex 6	Version 1.0	Schedule of Payments/Financial Report
Annex 7	Version 1.0	List of Sites and Investigators
Annex 8	Version	Quality of Life Questionnaire
Annex 9	Version	Quality of Life - Hand-Foot Syndrome
Annex 10	Version 4.0_July 2014	Serious Adverse Event Report Form
Annex 11	N/A	Summary of Product Characteristics for Sutent, Votrient and Nexavar

ANNEX 6: SCHEDULE OF STUDY PAYMENTS

Financial Report attached as a separate document

ANNEX 8: FACIT-FATIGUE QUALITY OF LIFE QUESTIONNAIRE

Escala FACIT de fatiga (Versión 4)

A continuación encontrará una lista de afirmaciones que otras personas con su misma enfermedad consideran importantes. Marque un solo número por línea para indicar la respuesta que corresponde a los últimos 7 días.

		Nada	Un poco	Algo	Mucho	Muchí- simo
187	Me siento agotado(a)	0	1	2	3	4
HI 12	Siento debilidad en todo el cuerpo	0	1	2	3	4
Anl	Me siento decaido(a)	0	1	2	3	4
An2	Me siento cansado(a)	0	1	2	3	4
An3	Tengo dificultad para comenzar las cosas porque estoy cansado(a)	0	1	2	3	4
An4	Tengo dificultad para terminar las cosas porque estoy cansado(a)	0	1	2	3	4
An5	Tengo energía	0	1	2	3	4
An7	Soy capaz de hacer mis actividades habituales (trabajar, ir a la escuela, hacer las compras)	0	1	2	3	4
An8	Necesito dormir durante el día	0	1	2	3	4
An 12	Estoy demasiado cansado(a) para comer	0	1	2	3	4
An 14	Necesito ayuda para hacer mis actividades habituales	0	1	2	3	4
An 15	Estoy frustrado(a) porque estoy demasiado cansado(a) para hacer las cosas que quiero hacer	0	1	2	3	4
An 16	Tengo que limitar mis actividades sociales debido al cansancio	0	1	2	3	4

Spanish (Universal) Copyright 1987, 1997 17 December 2010 Page 1 of 1

ANNEX 9. QUALITY OF LIFE HAND-FOOT SYNDROME

	SK	in and subcutaneous tis			
			Grade		
Adverse Event	1	2	3	4	5
Hypertrichosis	Increase in length, thickness or density of hair that the patient is either able to camouflage by periodic shaving or removal of hairs or is not concerned	Increase in length, thickness or density of hair at least on the usual exposed areas of the body [face (not limited to beard/moustache area)	-		-
	enough about the overgrowth to use any form of hair removal	plus/minus arms] that requires frequent shaving or use of destructive means of hair removal to camouflage; associated with psychosocial impact			
Definition: A disorder characteri	zed by hair density or length beyon	d the accepted limits of normal in	a particular body region, for a part	icular age or race.	
Hypohidrosis	-	Symptomatic; limiting instrumental ADL	Increase in body temperature; limiting self care ADL	Heat stroke	Death
Definition: A disorder characteri					
Lipohypertrophy	Asymptomatic and covering <10% BSA	Covering 10 - 30% BSA and associated tenderness; limiting instrumental ADL	Covering >30% BSA and associated tenderness and narcotics or NSAIDs indicated; lipohypertrophy; limiting self care ADL	-	-
Definition: A disorder characteri	zed by hypertrophy of the subcutan	eous adipose tissue at the site of	multiple subcutaneous injections	of insulin.	
Nail discoloration	Asymptomatic; clinical or diagnostic observations only; intervention not indicated	-	-	-	-
Definition: A disorder characteri	zed by a change in the color of the	nail plate.			
Nail loss	Asymptomatic separation of the nail bed from the nail plate or nail loss	Symptomatic separation of the nail bed from the nail plate or nail loss; limiting instrumental ADL	-	-	-
Definition: A disorder characteri	zed by loss of all or a portion of the	nail.			
Nail ridging	Asymptomatic; clinical or diagnostic observations only; intervention not indicated	-	-	-	-
Definition: A disorder characteri	zed by vertical or horizontal ridges	on the nails.			
Pain of skin	Mild pain	Moderate pain; limiting instrumental ADL	Severe pain; limiting self care ADL	-	-
Definition: A disorder characteri	zed by marked discomfort sensation	n in the skin.			
Palmar-plantar erythrodysesthesia syndrome	Minimal skin changes or dermatitis (e.g., erythema, edema, or hyperkeratosis) without pain	Skin changes (e.g., peeling, blisters, bleeding, edema, or hyperkeratosis) with pain; limiting instrumental ADL	Severe skin changes (e.g., peeling, blisters, bleeding, edema, or hyperkeratosis) with pain; limiting self care ADL	-	-
Definition: A disorder characteri	zed by redness, marked discomfort	, swelling, and tingling in the palm	s of the hands or the soles of the	feet.	
Periorbital edema	Soft or non-pitting	Indurated or pitting edema; topical intervention indicated	Edema associated with visual disturbance; increased intraocular pressure, glaucoma or retinal hemorrhage; optic neuritis; diuretics indicated; operative intervention indicated		-
Definition: A disorder characteri	zed by swelling due to an excessive	e accumulation of fluid around the			
Photosensitivity	Painless erythema and erythema covering <10% BSA	Tender erythema covering 10 - 30% BSA	Erythema covering >30% BSA and erythema with blistering; photosensitivity; oral corticosteroid therapy indicated; pain control indicated (e.g., narcotics or NSAIDs)	Life-threatening consequences; urgent intervention indicated	Death

